The 3-hydroxy-3-methylglutaryl-CoA reductase inhibitors or statins are recommended and have been widely used since the '80s for the primary and secondary prevention of cardiovascular diseases (NICE 2014). It is now established that these medications have significant anti-inflammatory effects that are independent from their lipid-lowering properties (Jain-2005), as well as appearing early in treatment only after seven day of administration (Macin-2011). Statins are considered extremely safe drugs: their more common side-effect are muscle pain or weakness (usually mild and quickly responding to stopping or switching medication) and elevation of liver transaminases (significant only in case of pre-existing hepatic disease), whereas more serious adverse events include rhabdomyolysis (very rare but severe myopathy associated with elevated creatine kinase and myoglobinuria), new-onset diabetes mellitus (in predisposed individual with pre-existing hyperglycaemia), and haemorrhagic stroke (in patients with prior haemorrhagic stroke or lacunar infarct); however, clinical trials have ultimately concluded that such adverse events attributed to statin therapy in routine practice are not actually

caused by it (Collins-2016), especially at doses lower than 80mg/day and when used for less than 52 weeks (Li-2016). Other common ($\geq 1/100$, $< 1/10$) but usually mild side-effects include: nasopharyngitis, pharyngo-laryngeal pain, epistaxis, headache, and gastrointestinal disturbances (constipation, diarrhoea, flatulence, dyspepsia, nausea). Importantly, a potential antidepressant effect for statins has been confirmed in animals (Kilic-2012), as well as clinically in observational (Parsaik-2014) and interventional studies (Salagre-2016). Although their anti-inflammatory and anti-oxidant properties have been involved, the mechanisms underlying the antidepressant effects of statins remain unclear, therefore further translational studies have been advocated in order to elucidate this aspect (Köhler-Forsberg-2017).

In this exploratory study, we will investigate the effect of seven-day administration of atorvastatin 20mg once daily compared to placebo on emotional and reward processing tasks in 50 healthy volunteers. In view of the previous evidence that statins may exert antidepressant effects via anti-inflammatory and anti-oxidant pathways, we predict that atorvastatin will have positive effect on emotional and reward processing.

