6. STUDY PROCEDURES

Baseline Assessments and Procedures

Individuals who are interested in participating in the study will be invited to attend a Screening Visit (maximum 2 hours) at the Neurosciences Building, Warneford Hospital.

Demographic information will be collected:

- Age (years, months), years in full-time education

Participants' eligibility to take part will be checked by recording the following:

- Weight, height, and BMI
- Medical history (including family psychiatric history), details of current and past medication
- Current and prior use of drugs (to exclude for drug use in the three months prior to the study)
- Menstrual cycle (in order to avoid scheduling testing in the premenstrual week)
- SCID-5 interview (Structured Clinical Interview for DSM-5) to probe for current or past psychiatric illness
- Urine pregnancy test (female participants only)

The following baseline assessments will be completed (APPENDIX F: QUESTIONNAIRES):

- Beck Depression Inventory (BDI)
- Eysenck Personality Questionnaire (EPQ)

- Positive and Negative Affect Schedule (PANAS)
- Side-effects questionnaire (to determine baseline of bodily symptoms/'side-effects')
- Snaith-Hamilton Pleasure Scale (SHAPS)
- State and Trait Anxiety Inventory (STAI)
- Visual Analogue Scales (VAS) measuring subjective state

Also, phlebotomy will be undertaken to obtain a sample of:

- high sensitivity-C Reactive Protein

Participants will be asked to wait while their eligibility to take part is assessed by a medical doctor involved in the study (maximum 30 minutes). Any participant for whom additional information is required before an eligibility judgment can be made will be asked to return on a different day once this information has been obtained.

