The randomisation code will be broken if a participant requires treatment for a new medical condition or experiences serious adverse reactions and either of these situations make it clinically important to know what medication they are taking. A 24/7 emergency mobile contact number will be provided on a wallet-sized card given to participants during their Research Visit. The research team member on-call will be able to contact the medical supervisor and they will make the decision to unblind. In order to unblind the participant, the medic will access the list kept in a secure cabinet at the Neurosciences Building and will disclose the allocation within a maximum of one hour. If breaking the code is necessary, only the individual's code will be broken. Data from unblinded participants will not be admitted to analysis. If unblinding occurs, the researcher will record the reason and result of the unblinding, as well as the date and time of the event.

During the week of drug/placebo administration, participants will be advised not to drink alcohol and not to carry out activities requiring full alertness, such as driving, if they are aware of any impairment. During this week, a researcher will phone up the participant on day 2 and day 4 to check that there are no concerns. Additionally,

participants will receive a text message every day reminding them to take the study medication. They will have the 24-hour contact phone number of a member of the study team and be encouraged to get in contact if they have any concerns or queries during the study week, or if their medication or health status changes.

Subsequent Visits

The Research Visit (approximately 2 hours) will take place after day 7 of atorvastatin/placebo administration. This visit will involve administration of behavioural tasks measuring emotional and reward processing. It will take place at the Neurosciences Building, Warneford Hospital.

Participants will complete the following questionnaires before the behavioural tasks:

- Positive and Negative Affect Schedule (PANAS)
- Side-effects questionnaire
- State Anxiety Inventory (state-STAI)
- Visual Analogue Scales (VAS)

Also, phlebotomy will be repeated to obtain a sample of:

- high sensitivity-C Reactive Protein

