Statins are considered extremely safe drugs: their more common side-effect are muscle pain or weakness (usually mild and quickly responding to stopping or switching medication) and elevation of liver transaminases (significant only in case of pre-existing hepatic disease), whereas more serious adverse events include rhabdomyolysis (very rare but severe myopathy associated with elevated creatine kinase and myoglobinuria), new-onset diabetes mellitus (in predisposed individual with pre-existing hyperglycaemia), and haemorrhagic stroke (in patients with prior haemorrhagic stroke or lacunar infarct); however, clinical trials have ultimately concluded that such adverse events attributed to statin therapy in routine practice are not actually caused by it (Collins-2016), especially at doses lower than 80mg/day and when used for less than 52 weeks (Li-2016). Other common ($\geq 1/100$, $< 1/10$) but usually mild side-effects include: nasopharyngitis, pharyngo-laryngeal pain, epistaxis, headache, and gastrointestinal disturbances (constipation, diarrhoea, flatulence, dyspepsia, nausea). The potential side-effects and adverse events will be clearly stated in the Participant Information Sheet and researchers will discuss these with participants as part of the informed consent procedure.

To minimise the risk associated with side-effects, participants will be contacted on days 2 and 4 of the study week by a named researcher to check there are no concerns. All participants will have 24-hour contact details of a named researcher who they can contact during the study period. The named researcher will in turn contact a qualified medical doctor if necessary. In order to limit the risks associated with fatigue, during the week of statin/placebo administration, participants will be advised not to drink alcohol, and not to carry out activities requiring full alertness if they are aware of any impairment.

If judged necessary by the medical lead, the randomisation code will be broken for that individual by the medical supervisor and the participant will be advised to stop taking the medication and withdrawn from the study.

Will the research involve deliberate deception of participants?
 
If yes, justify why deception is used, describe deception and debriefing process, and include debriefing documents in the application
	Yes 	No 
---	------------------------------	--

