9. STATISTICS AND ANALYSIS

Do you have a statistical plan?

Yes No

If no, please justify.

The IBM SPSS statistical software will be used to analyse all behavioural data. Demographic and baseline measures will be analysed using independent t-tests.

Mood, anxiety, side-effects, and hs-CRP measures will be analysed using repeated measures analysis of variance (ANOVA).

Behavioural task results will be analysed using between-groups analysis of variance (ANOVA).

Any significant interactions will be followed up using simple main effect analyses. When assumptions of equality of variances are not fulfilled, the Greenhouse-Geisser procedure will be used to correct the degrees of freedom.

Number of Participants

50 healthy volunteers (25 per group)

Have you done a sample size calculation?

Yes No

If yes, please give details below

If no, please give details to indicate you have considered the implications the selected sample size will have on the study outcome

We will be using the Oxford Emotional Test Battery, which is a well-validated set of emotional processing tasks that are sensitive to antidepressant effects. On the facial expression recognition task, one of the main outcome variables is accuracy at recognising fearful facial expressions and a sample size of 25 per group would give 0.9 power to detect changes of the magnitude of those we have seen in a previous antidepressant healthy volunteer study [drug mean 10.64 (SD 9.77) vs placebo mean 3.36 (SD 5.96) (Harmer-2004).

Analysis of Outcome Measures

Data analysis will take place at the University of Oxford, Department of Psychiatry, and will be undertaken by the research team under the supervision of the Principal Investigator. All data will be analysed using a between-groups analysis of variance (ANOVA).

Withdrawn participants' data will not be included in the analysis.

The primary outcome measure is performance (accuracy and reaction time) in computer-based tasks of emotional processing in the comparison between drug and placebo groups. Secondary to this is performance (accuracy and reaction time) in a computer-based task of reward processing in the comparison between drug and placebo groups, and changes in high sensitivity-C Reactive Protein (hs-CRP) from baseline to seven-day in the comparison between drug and placebo groups.

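### Side-effects go to repeated measures ANOVA with no symptom counts or intervals planned; with 25 per arm and uncommon symptoms, per-symptom counts with exact intervals would say more than an item-level test

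*Combined protocol and SAP*

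**What the plan says.** Section 9 (Statistics and Analysis) groups side-effects with mood, anxiety and hs-CRP: "Mood, anxiety, side-effects, and hs-CRP measures will be analysed using repeated measures analysis of variance (ANOVA"). A later sentence in the same section sends all data to between-groups ANOVA. Neither sentence mentions counts, percentages or confidence intervals for individual symptoms.

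The data come from a questionnaire given twice. At screening, Section 6 lists "Side-effects questionnaire (to determine baseline of bodily symptoms/'side-effects". After day 7 it appears again under "Participants will complete the following questionnaires before the behavioural tasks". Its items and scoring belong to Appendix F, which is not part of the text available here. The sample is "50 healthy volunteers (25 per group").

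On frequency, Sections 4 and 8 give a band of at least 1/100 and below 1/10 for a set of other common effects, "but usually mild side-effects include: nasopharyngitis, pharyngo-laryngeal pain, epistaxis, headache" and five gastrointestinal complaints: nine symptoms in all. For statins generally, Section 8 says "their more common side-effect are muscle pain or weakness", with no figure. Side-effects are not among the primary or secondary outcomes in Sections 2 and 9.

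**The concern.** With two visits, the group-by-time test of a repeated measures ANOVA is the same as a t-test on change from screening. That test compares mean changes and relies on roughly normal errors. If each symptom affects only a few of 25 people, most item change scores are zero, and the test is a poor summary of them.

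Two things are at stake. A non-significant p-value hides how little 25 per arm can exclude, whereas a count with an interval shows it. Knowing which symptoms occurred in which arm also helps interpret two other parts of the study: the treatment guess collected at the Research Visit to assess blinding, and the reaction times that form part of the primary outcome. A mean-score F test does not supply that information.

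**Working it through.** **The plan's own figure.** The only power stated is 0.9, for fearful-face accuracy, from "drug mean 10.64 (SD 9.77) vs placebo mean 3.36 (SD 5.96"). The difference is 10.64 − 3.36 = 7.28 and the pooled SD is √((9.77² + 5.96²)/2) = 8.09, so d = 0.90. With 25 per arm and two-sided alpha 0.05 (assumed; the plan states none), power is Φ(0.90 × √12.5 − 1.96) = 0.889 by the normal approximation. The figure reproduces, but it says nothing about side-effects.

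**Expected counts on drug, per symptom** (n = 25, Section 9; rates from Sections 4 and 8):

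| Rate | Expected, 25 × rate | P(nobody affected), (1 − rate)^25 |
|---|---|---|
| 1% | 0.25 | 0.78 |
| 5% | 1.25 | 0.28 |
| 10% (edge of band) | 2.5 | 0.07 |

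These are expectations. At 10% the central 95% range of the observed count is 0 to 6, and the chance of more than 3 is 0.24.

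**Item-level test.** Assume present/absent scoring, no symptom at screening, two-sided alpha 0.05. With a of 25 affected on drug and none on placebo, x = a/25, pooled variance v = 25x(1 − x)/48, and t = x/√(2v/25) on 48 degrees of freedom.

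- a = 3: x = 0.12, v = 0.055, t = 1.81, p = 0.077.
- a = 4: x = 0.16, v = 0.070, t = 2.14, p = 0.038.

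At least 4 v 0 is therefore needed. For 10% v 0%, power = P(X ≥ 4 | 25, 0.10) = 0.24. Summing over all pairs of counts gives the other cases:

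| Drug v placebo | ANOVA-equivalent t-test | Fisher's exact test |
|---|---|---|
| 10% v 0% | 0.24 | 0.03 |
| 10% v 1% | 0.19 | 0.03 |
| 10% v 5% | 0.08 | 0.01 |
| 5% v 0% | 0.03 | 0.001 |

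Placebo rates are not in the documents; 0% to 5% is an assumed range. With assumed 1-2 point severity scores, power at 10% v 0% is about 0.15.

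**Type I error of the t-test.** It is 0.02 at 5% in both arms and 0.0002 at 1% in both arms. At 10% in both arms the same enumeration gives 0.049, so the shortfall applies in the lower part of the band. At 1% in both arms nobody is affected with probability 0.99^50 = 0.605, and the F test is then undefined.

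**Sample size for one symptom at 80% power:** 100 per group for 10% v 1%, and 435 per group for 10% v 5%.

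**Total score.** The answer depends on scoring that the text does not give. All figures here are simulations under assumed questionnaires.

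- Scores of 1-2 points, nine items raised by 9 points: about 0.51 (15 items, 5% background) and 0.28 (20 items, 10% background).
- The same two set-ups with one item raised by 10 points: 0.05 to 0.06.
- Twelve items scored 0-3, nine raised by just under 10 points: about 1.0 with no background symptoms, 0.52 at 10%, 0.30 at 20% and 0.18 at 30%.

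**What counts would show.** For 0/25 the exact two-sided 95% upper limit is 1 − 0.025^(1/25) = 13.7%. For 2/25 the exact interval is 1.0% to 26.0%. Seeing no case on drug would not exclude any rate in the protocol's common band.

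**The case against.** The strongest reply is that ANOVA is not to blame. Low power comes from 25 per arm and rare events, and Fisher's exact test does worse at every rate tabulated above. This stands: changing the test would gain nothing, and the recommended change detects nothing that the ANOVA would miss. It improves what is reported.

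A reader might infer that a null result is to be expected whether or not the drug causes symptoms. That does not hold for a total score. If many symptoms rise together against little background, power can be substantial, and the 0.05 to 0.06 figure applies only when a single item is raised.

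A reader might also infer that every symptom will affect 0 to 3 of 25 people. The band covers only the nine other common effects, and muscle pain or weakness is called more common without a rate. The band also describes reactions on drug, whereas the questionnaire is given at screening to capture background symptoms, so reports may be more frequent.

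Finally, a reader might infer that a null will be presented as good tolerability. No passage says so. Side-effects are not a listed outcome, and Section 2 says the study does not fit a definition that includes identifying or comparing adverse reactions. Blinding is checked directly by the treatment guess, concerns are sought by calls on days 2 and 4, and planning an ANOVA does not prevent the team from tabulating counts. These points keep the matter minor. They do not supply the missing summary.

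**Conclusion.** The point holds as a low-cost improvement. The plan names a mean-score test for side-effects and no symptom-level summary. For the nine symptoms with a stated rate, 0.25 to 2.5 affected people of 25 are expected per symptom, and item-level power is at most about 0.24. That ceiling assumes present/absent scoring, no baseline symptoms, two-sided alpha 0.05 and no cases on placebo; other placebo rates lower it. Type I error falls well short of 0.05 at rates of 5% or less, but is close to nominal at 10%.

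The documents do not support saying that the ANOVA will miss drug effects in general. How the questionnaire is scored, and whether items or a total are analysed, cannot be settled from the available text. What can be said is that a non-significant result, by item or in total, would not be evidence of no side-effects. No conclusion on the primary or secondary outcomes depends on this.

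**What to change.** In Section 9, take side-effects out of the ANOVA sentence and add text to this effect: for each questionnaire symptom, report the number and percentage of participants with a new or worse symptom than at screening, by arm, with exact 95% confidence intervals and the between-arm difference, and no item-level significance test. Add that 0/25 is compatible with a rate up to about 14%, and that a non-significant result is not evidence of no side-effects.

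State how the questionnaire is scored. The ANOVA may stay for a total score as a supporting summary; if so, reconcile the repeated measures sentence with the later one that sends all data to between-groups ANOVA. Give the denominator for the table, because Sections 6 and 9 exclude withdrawn and unblinded participants from the analysis.

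The cost is a short edit and one extra table from data already collected. The downside is that there is no p-value per symptom.

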- Loss to follow up

If a participant is withdrawn, no further procedures or observations will continue to be required. Withdrawal from the study will result in exclusion of the data for that participant from the analysis. Withdrawn participants will be replaced. The reason for withdrawal, if given, will be recorded in the Participant Log of the Research Master File.

Definition of End of Study

The end of the study for participant involvement is the date of the last visit of the final participant.

Expenses and Benefits

Participants will be paid £100 upon completion of their participation in the research. In addition, they may win up to £10 depending on the choices they make in the reward task (see 'Subsequent Visits' above). If they do not complete the study, they will be given a pro-rata amount to recompense the time they did spend in the study. Reasonable travel expenses for any visits will be reimbursed on production of receipts, or a mileage allowance provided as appropriate.

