A serious adverse event (SAE) occurring to a participant should be reported to CTRG and the Medical Sciences IDREC where, in the opinion of the Principal Investigator, the event was ‘related’ (resulted from administration of any of the research procedures) and ‘unexpected’ (the type of event is not listed in the protocol as an expected occurrence). Reports of related and unexpected SAEs should be submitted within 15 days of the Principal Investigator becoming aware of the event. For fatal and life-threatening SUSARs, this will be done no later than 7

calendar days after the Sponsor or delegate is first aware of the reaction. Any additional relevant information will be reported within 8 calendar days of the initial report.

c) Safety of Participants

What level of baseline screening will take place for this study?

All participants will undergo a Screening Visit to ensure only eligible participants take part. The following will be recorded at baseline screening:

- Demographic information (age [years, months], years in full-time education)
- Number of cigarettes smoked per day, units of alcohol consumed per week, caffeinated drinks consumed per day
- Current and prior use of drugs (to exclude for drug use in the three months prior to the study)
- SCID-5 interview (Structured Clinical Interview for DSM-5) to probe for current or past psychiatric illness
- Beck Depression Inventory (BDI)
- Eysenck Personality Questionnaire (EPQ)
- State and Trait Anxiety Inventory (STAI)
- Positive and Negative Affect Schedule (PANAS)
- Snaith-Hamilton Pleasure Scale (SHAPS)
- Side-effects questionnaire
- Visual Analogue scales (VAS)

To ensure it is safe to administer the drug to the participant, the following will be recorded:

- Weight, height, and BMI
- Medical history (including family psychiatric history)
- Details of current and past medication
- Urine pregnancy test (female participants only)

Also, phlebotomy will be undertaken to obtain a sample of:

- high sensitivity-C Reactive Protein

Participation in prior studies will be recorded to exclude for individuals who have used the same/similar emotional processing tasks.

Provide details about the safety monitoring of participants and the staff/researchers carrying this out

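### The only planned side-effects analysis covers completers who stayed blinded, so a dosed volunteer removed because of a reaction appears in no planned by-arm summary

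*Combined protocol and SAP*

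**What the plan says.** All references are to the combined protocol and SAP.

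- **Analysis.** Section 9 states: "Mood, anxiety, side-effects, and hs-CRP measures will be analysed using repeated measures analysis of variance (ANOVA". It plans no other summary of side-effects or adverse events. The side-effects questionnaire is completed at the Screening Visit and again at the Research Visit after day 7 (Section 6).
- **Withdrawal.** Section 6, under Discontinuation/Withdrawal, states: "Withdrawal from the study will result in exclusion of the data for that participant from the analysis. Withdrawn participants will be replaced". The same paragraph asks for nothing more from a participant once withdrawn. Section 9 repeats the exclusion under Analysis of Outcome Measures.
- **Unblinding.** Section 6 gives two grounds for breaking the code. One is a newly arisen illness that needs treating. The other is that the volunteer "experiences serious adverse reactions and either of these situations make it clinically important to know what medication they are taking". The same paragraph states: "Data from unblinded participants will not be admitted to analysis". Section 8 d) adds that, after a code-break the medical lead judges necessary, "the participant will be advised to stop taking the medication and withdrawn from the study".
- **Records kept.** Section 6 states: "The reason for withdrawal, if given, will be recorded in the Participant Log of the Research Master File". At a code-break, "the researcher will record the reason and result of the unblinding, as well as the date and time of the event". Each allocation is on the Randomisation List (Section 6). Under Section 8 b), a serious adverse event "should be reported to CTRG and the Medical Sciences IDREC where, in the opinion of the Principal Investigator, the event was" both related and unexpected.
- **Purpose.** The Synopsis says that the study is not one designed to compare the drug's adverse reactions. Side-effects are not among its listed outcome measures.

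**The concern.** The sponsor chose to measure side-effects before and after treatment and to compare the arms on them. The rules for who enters that comparison depend partly on the thing being compared. A serious reaction is a stated ground for unblinding, unblinding bars the data, and a code-break judged necessary by the medical lead also leads to withdrawal, which bars the data again. Someone who withdraws of their own accord because of a symptom is barred in the same way.

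Replacement then refills the group, so the number analysed does not show that anyone left. What is at stake is the reading of the tolerability result. It would be a statement about those who completed without unblinding, but nothing in the plan labels it so or sets beside it a count of who left each arm and why.

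**Working it through.** **1. The plan's own figures.** The documents give no expected number of reactions, withdrawals or unblindings, so there is no figure on this point to reproduce. The one calculated figure in Section 9 is 0.9 power for fearful-face accuracy with 25 per group. Difference = 10.64 − 3.36 = 7.28. SD = √((9.77² + 5.96²)/2) = 8.09. The ratio is 0.90, and 0.90 × √12.5 = 3.18. With two-sided alpha 0.05 (assumed; none is stated), 3.18 − 1.96 = 1.22, which gives power 0.889 by the normal approximation. A two-sided t calculation gives 0.876. The stated figure is about right and does not bear on this point.

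**2. Who reaches the side-effects ANOVA.** Setting the rules side by side:

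| Situation | Day-7 questionnaire | Barred by a rule | In the ANOVA |
|---|---|---|---|
| Reaction, attends day 7, neither unblinded nor withdrawn | Yes | No | Yes |
| Stops capsules, not withdrawn, attends day 7 | Yes | No | Yes |
| Withdraws mid-week because of a reaction | Normally none | Yes | No |
| Code broken mid-week for a serious reaction, then withdrawn | Normally none | Yes, twice | No |
| Completes day 7, then withdrawn or unblinded | Yes | Yes | No |

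The second row stands because Section 6 says only that the Investigator may discontinue a participant; stopping capsules is not itself withdrawal. In the third and fourth rows the missing second score would keep the person out of a two-time-point comparison even without the exclusion rules. The rules alone do the removing in the last row, or if someone unblinded mid-week nonetheless attended day 7.

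**3. Size, by assumption.** Let w dosed people leave one arm because of a reaction, all replaced in that arm, with no leavers in the other arm. Section 6 says that withdrawals are replaced but does not say that the replacement joins the same arm, so that is also an assumption. The share of those dosed in that arm who are missing from the ANOVA is w/(25 + w). The test column compares this with 0/25.

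| w | Missing share | Exact 95% CI | Two-sided Fisher p |
|---|---|---|---|
| 0 | 0/25 = 0% | 0% to 13.7% | 1.00 |
| 1 | 1/26 = 3.8% | 0.1% to 19.6% | 1.00 |
| 2 | 2/27 = 7.4% | 0.9% to 24.3% | 0.49 |
| 3 | 3/28 = 10.7% | 2.3% to 28.2% | 0.24 |

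**4. How likely at least one is.** If each of 25 drug-arm volunteers has chance p of a reaction that ends in withdrawal or unblinding, the chance of at least one is 1 − (1 − p)^25. For p = 1%, 2%, 5% and 10% (assumed values) this is 22%, 40%, 72% and 93%.

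**5. What follows.** The numbers are too small for a between-arm test. A listing of leavers can inform a reader but cannot establish a difference.

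**The case against.** The strongest reply is that this is a gap in reporting rather than a faulty analysis. Most of the people concerned would have no day-7 score, so deleting the exclusion rules would not bring them into the ANOVA. The questionnaire is given with the mood and anxiety scales just before the tasks. It can reasonably be read as describing participants' state at testing, for which those tested are the right population; the protocol does not say so, however. The trigger for unblinding is narrow, and ordinary side-effects in people who complete are analysed. The study disclaims any aim of comparing adverse reactions.

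Most of this stands. It is why the ANOVA should be kept and why the point is small. It does not remove the point: the exclusion rules are general, they make no exception even for a descriptive account, and no by-arm summary of the leavers is planned.

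Three stronger readings are tempting and are not supported:

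- *Reactions among leavers are lost, or a reader could never learn who left and why.* Withdrawal reasons (if given), unblinding reasons and results, and allocations are all recorded, so a by-arm listing could be made from them. The plan just does not provide for one.
- *Anyone who stops the capsules disappears.* Such a person may remain in the study and be analysed.
- *The ANOVA would be repaired by dropping the exclusions.* It would not, for want of a second measurement.

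**Conclusion.** The concern holds, and it is minor. As written, the side-effects ANOVA describes completers who were not unblinded. A serious reaction that leads to a code-break and withdrawal can take a dosed volunteer out of that comparison because of the reaction. This follows from the stated rules and needs no numerical assumption.

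Its practical size is unknown. The number of such leavers may be zero, and the 3.8% to 10.7% range rests on 1 to 3 leavers in one arm, all replaced in that arm. A reader might infer that the plan conceals harm or that the main results are at risk. The documents support neither: individual records are kept, and this point leaves emotional processing, reward processing and hs-CRP untouched.

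**What to change.** Keep the repeated measures ANOVA and state in Section 9 that, for side-effects, it covers participants who completed and were not unblinded.

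Add to the exclusion sentences in Section 6 (code-breaking and withdrawal) and Section 9 an exception along these lines: *except for one descriptive by-arm listing, unless the participant asks for their data to be removed*. The listing should:

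- cover all randomised participants given study capsules, noting where none is known to have been taken, since adherence is asked about only at the Research Visit;
- show each withdrawal and unblinding with its reason, and any adverse event already recorded;
- be prepared after the code is opened, be labelled descriptive, and carry no between-arm test.

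Noting symptoms volunteered on the day 2 and day 4 calls would be useful but is optional. It is new recording, because the plan describes no log of what is said on those calls.

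The cost is one small table, a short protocol amendment submitted for approval under Section 12, and possibly a check that the information sheet's wording on withdrawn data allows the listing. No new visit or instrument is needed.
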